4 SELECTION AND WITHDRAWAL OF PATIENTS

4.1 Inclusion Criteria

The population for this study is male and female patients ≥ 18 years of age who have met the diagnostic criteria for HeFH outlined by the Simon Broome Register Group (Appendix C) World Health Organization (WHO)/Dutch Lipid Network (score >8 ; Appendix D).

Patients who meet all of the following criteria will be eligible to participate in the study:

1. Must be willing to participate in the study and provide written informed consent;
2. Male and female adults ≥ 18 years of age;
3. Female patients of child bearing potential with negative serum pregnancy (beta human chorionic gonadotropin) test who are not breastfeeding, do not plan to become pregnant during the study, and agree to use effective birth control (ie, condoms, diaphragm, non-hormonal intrauterine device [IUD], or sexual abstinence [only if this is in line with the patient's current lifestyle]) throughout the study and for at least 1 month after study completion; hormonal contraception (estrogens stable ≥ 3 months) and hormonal IUDs are permitted if used with a secondary birth control measure (eg, condoms); OR female patients of non-child bearing potential (ie, surgically [bilateral oophorectomy, hysterectomy, or tubal ligation] or naturally sterile [>12 consecutive months without menses]); male patients who have sexual intercourse with a female partner of child bearing potential from the first dose of study drug until 1 month after study completion must either be surgically sterile (confirmed by documented azoospermia >90 days after the procedure) OR agree to use a condom with spermicide. All male patients must agree not to donate sperm from the first dose of study drug until 1 month after study completion;
4. Must have a diagnosis of HeFH by genetic testing or by having met the diagnostic criteria for definite familial hypercholesterolemia outlined by the Simon Broome Register Group (Appendix C) or WHO/Dutch Lipid Network (score >8 ; Appendix D);
5. Must have a fasting LDL-C ≥ 2.6 mmol/L (100 mg/dL); and
6. Must be on a stable or maximally tolerated dose (≥ 4 weeks prior to screening) of an approved statin (rosuvastatin ≤ 20 mg daily, atorvastatin ≤ 80 mg daily), with or without ezetimibe.

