9.1.1 Adverse (Drug) Reaction

All noxious and unintended responses to a medicinal product related to any dose should be considered an adverse drug reaction. “Responses” to a medicinal product means that a causal relationship between a medicinal product and an adverse event is at least a reasonable possibility, ie, the relationship cannot be ruled out.

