9.1.3 Assessment of Adverse Events by the Investigator

The Investigator will assess the severity (intensity) of each adverse event as mild, moderate, or severe, and will also categorize each adverse event as to its potential relationship to study drug using the categories of yes/no.

Assessment of Severity:

Mild – An event that is easily tolerated and generally not interfering with normal daily activities.

Moderate – An event that is sufficiently discomforting to interfere with normal daily activities.

Severe – An event that is incapacitating with inability to work or perform normal daily activities.

Causality Assessment:

The relationship of an adverse event to the administration of the study drug is to be assessed according to the following definitions:

No (unrelated, not related, no relation) – The time course between the administration of study drug and the occurrence or worsening of the adverse event rules out a causal relationship and another cause (concomitant drugs, therapies, complications, etc.) is suspected.

Yes (related) – The time course between the administration of study drug and the occurrence or worsening of the adverse event is consistent with a causal relationship and no other cause (concomitant drugs, therapies, complications, etc.) can be identified.

The definition implies a reasonable possibility of a causal relationship between the event and the study drug. This means that there are facts (evidence) or arguments to suggest a causal relationship.

The following factors should also be considered:

- The temporal sequence from study drug administration-
 - The event should occur after the study drug is given. The length of time from study drug exposure to event should be evaluated in the clinical context of the event.
- Underlying, concomitant, intercurrent diseases-
 - Each report should be evaluated in the context of the natural history and course of the disease being treated and any other disease the patient may have.
- Concomitant drug-
 - The other drugs the patient is taking or the treatment the patient receives should be examined to determine whether any of them might be recognized to cause the event in question.
- Known response pattern for this class of study drug-
 - Clinical and/or preclinical data may indicate whether a particular response is likely to be a class effect.
- Exposure to physical and/or mental stresses-

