3.8.1 Adverse Events

Treatment-Emergent Adverse Events (TEAEs) are defined as adverse events that are new or worsen after the first dose of study drug. AE worsening applies to severity or relationship to study drug.

A summary overview of TEAEs will be provided, which presents the number and percentage of patients in each treatment group from the Safety Population satisfying each of the following categories:

- Any TEAEs,
- Maximum severity of TEAEs,
- Study drug-related TEAEs,
- Maximum severity of study drug-related TEAEs,
- All treatment-emergent serious adverse events (SAEs),
- All study drug-related TE-SAEs,
- TEAEs leading to death,
- TEAEs leading to study drug discontinuation, and
- Study drug-related TEAEs leading to study drug discontinuation.

Adverse events will be coded using MedDRA. The number and percentage of patients with TEAEs will be summarized by their MedDRA preferred term within system organ class and by treatment. AEs will be counted by the number of events as well as the number of patients. For event count summaries, multiple AE events with the same MedDRA coded terms (preferred term and system organ class) and onset date and time from the same patient will only be counted once. For patient count summaries, multiple AE events with the same MedDRA coded terms (preferred term and system organ class) from the same patient will only be counted once.

The number and percentage of patients with TEAEs will be summarized by reported maximum severity within each MedDRA preferred term within system organ class and by treatment.

The number and percentage of patients with TE-SAEs, any drug-related TEAEs, drug-related TE-SAEs, and TEAEs and TE-SAEs that lead to study drug discontinuation will be summarized by preferred term within system organ class and by treatment. In these summaries, any patients reporting multiple episodes of the same TEAE (i.e., same preferred term and system organ class) will be counted once.

All SAEs will be listed with an indication of whether the SAE was treatment emergent or started prior to treatment.

All TEAEs that are reported as leading to study drug discontinuation will be listed.

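### The yes/no causality definitions in Protocol 9.1.3 are not exhaustive and contradict 9.1.1: an event with plausible timing and another possible cause meets neither

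*Protocol*

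**What the plan says.** Protocol 9.1.3 asks the investigator to classify the "potential relationship to study drug using the categories of yes/no". The two categories are defined as follows:

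- *Yes*: the time course fits causation by study drug, and "no other cause (concomitant drugs, therapies, complications, etc.) can be identified".
- *No*: the time course "rules out a causal relationship and another cause (concomitant drugs, therapies, complications, etc.) is suspected".

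The text after these definitions describes them as implying a reasonable possibility of causation. It then lists factors to weigh, among them concomitant drugs, class effects and the study drug's pharmacology.

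Protocol 9.1.1 defines an adverse drug reaction by a different test. Causality need only be a reasonable possibility, which that section equates with "the relationship cannot be ruled out".

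Inclusion criterion 6 (Protocol 4.1) opens with "Must be on a stable or maximally tolerated dose" and names rosuvastatin or atorvastatin as the permitted statins. Protocol 1.2.1 reports that the study drug raised rosuvastatin exposure 1.8-fold at 200 mg per day (about 1.6-fold predicted at 100 mg) and atorvastatin exposure 1.35-fold at 100 mg per day.

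SAP 3.8.1 tabulates drug-related TEAEs and drug-related serious TEAEs, and includes a row for "Study drug-related TEAEs leading to study drug discontinuation". Under Protocol 9.3, an SAE arising after the 30-day follow-up period is reportable if the investigator considers it related.

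**The concern.** Each definition joins two conditions with *and*, so failing one definition does not mean meeting the other. The case left out is an ordinary one in medicated patients: the timing fits the study drug, but another drug could also explain the event.

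In this trial the obvious competing drug is the statin. Muscle symptoms, CK rises and transaminase rises are events that a statin could explain. The protocol itself gives reasons to watch them: section 1.1.2 reviews liver-enzyme elevations with earlier thyroid agonists, and section 1.2.3 lists liver and muscle effects for DSMB review. Because the study drug raises statin exposure, a statin-type event may itself be a consequence of study drug. The *Yes* wording nevertheless treats an identified concomitant drug as a reason to withhold *Yes*.

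What is at stake is whether the drug-related tables mean the same thing across the approximately 13 sites, and whether late SAEs reach the Sponsor on a consistent basis.

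**Working it through.** There is no figure to reproduce. The check is whether the definitions cover every case, and how 9.1.1 would treat the same cases.

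**Step 1: cross timing with alternative cause.** Treat an identified and a suspected alternative as the same state.

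| Time course | Other cause | 9.1.3 *Yes*? | 9.1.3 *No*? | 9.1.3 result | 9.1.1 standard |
|---|---|---|---|---|---|
| Consistent | Absent | Met | Not met | *Yes* | Reaction |
| Consistent | Present | Fails on other cause | Fails on timing | Neither | Reaction, if a reasonable possibility remains |
| Rules out | Present | Not met | Met | *No* | Not a reaction |
| Rules out | Absent | Fails on timing | Fails on other cause | Neither | Not a reaction |

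Two of the four combinations have no category. The second row is the one that matters clinically. Under 9.1.1 every row has an answer.

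**Step 2: separate suspected from identified.** *Yes* is blocked by a cause that can be identified, whereas *No* needs only one that is suspected. Read strictly, this gives three states of alternative cause (none, suspected only, identified) and 2 × 3 = 6 combinations.

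- Consistent timing: none gives *Yes*, suspected only gives *Yes*, identified gives neither.
- Timing rules causality out: none gives neither, suspected only gives *No*, identified gives *No*.

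Two of the six combinations still have no category. The gap for plausible timing narrows to an identified alternative but does not close.

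**Step 3: does the surrounding text repair it?** The reasonable-possibility sentence presents itself as a consequence of the definitions. It is not one, because a reasonable possibility can coexist with an identified alternative, and *Yes* excludes that. The section therefore holds two standards.

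**Step 4: trace what uses the call.**

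- Dependent: the drug-related TEAE, serious TEAE and discontinuation summaries (SAP 3.8.1), the relationship summaries (Protocol 10.2.2), and SAEs after the 30-day period (Protocol 9.3).
- Not dependent: TEAE tables for all new events by arm; ALT, AST, CK and GGT analyses and shift tables (SAP 3.8.2); liver follow-up triggered by laboratory values and symptoms (Protocol 9.13); and SAE reporting within 24 hours from consent to 30 days after the last dose (Protocol 9.3).
- One narrow exception: SAP 3.8.1 lets a worsening in relationship make a pre-existing event treatment-emergent.

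**The case against.** The strongest reply is that the documents do not show which way the ambiguity resolves, and that most safety information bypasses it. Three stronger readings are tempting, and the documents do not support them.

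**That related events will be under-counted.** A reader might infer this because *Yes* is so narrow. But *No* is narrow too: an event with plausible timing cannot literally be *No*. The reasonable-possibility sentence, the list of factors and 9.1.1 all lean towards *Yes*. Defaulting to *No* when the *Yes* test fails is a plausible habit, but it is an inference about behaviour.

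**That nearly every liver or muscle event is affected because all patients take a statin.** The rule asks whether another cause can be identified, not whether another drug is present. The statin dose must have been stable for at least 4 weeks before screening, and ALT above 1.5 × ULN or CK above 3 × ULN at entry is exclusionary. A new event after starting study drug does not automatically have the statin as an identified cause. In addition, SAP 3.4 provides for patients on no statin, so the accurate statement is that a statin is required at entry.

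**That expedited reporting hangs on the yes/no box.** Protocol 9.5 concerns suspected unexpected serious adverse reactions reported by the Sponsor, and 9.1.1 defines a reaction by the inclusive standard. Nothing makes the investigator's box the sole determinant.

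It is also fair to note that Protocol 1.2.1 mitigates the statin interaction by staggered dosing and a 20 mg rosuvastatin cap, and that 1.2.2 reports no myopathy with higher study-drug exposure. The trial is blinded and placebo-controlled, with statins required in both arms, so the comparison of all events by arm is the sounder safety evidence.

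These points limit the consequence. They do not close the gap or remove the contradiction between 9.1.3 and 9.1.1.

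**Conclusion.** The point holds as a defect in a stated rule, with limited reach. Section 9.1.3 forces a two-way call with definitions that leave out events having both plausible timing and another possible cause, and it contradicts 9.1.1. Events that a statin could also explain may be classed inconsistently or as unrelated.

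The effect falls on the drug-related summaries and on SAEs more than 30 days after the last dose. A liver or muscle signal would still be visible in the all-causality and laboratory results.

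The number of events affected cannot be derived from the documents. The conclusion assumes only that some events will have plausible timing and an identifiable alternative. It does not assume that being on a statin supplies that alternative, or that investigators will resolve the gap in one direction.

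**What to change.** Reconcile 9.1.3 with 9.1.1 under one standard:

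- *Yes*: there is a reasonable possibility that study drug caused or contributed to the event, even if another cause is also possible.
- *No*: there is no reasonable possibility that study drug caused or contributed to the event.

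The categories are then exhaustive, and the reasonable-possibility sentence and the factors that follow it agree with the definitions. The eCRF completion guidance should carry the same wording and say that an event a statin could explain may still be *Yes*.

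The cost is two sentences of protocol text plus the guidance. Design, sample size and efficacy analysis are untouched. The downside is that the count of related events may be slightly higher.

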9.2 Serious Adverse Events

An adverse event or adverse reaction is considered serious if, in the view of either the Investigator or Sponsor, it results in any of the following outcomes:

- Death;
- A life-threatening adverse event;
 - Note: An adverse event or adverse reaction is considered “life-threatening” if, in the view of either the Investigator or Sponsor, its occurrence places the patient at immediate risk of death. It does not include an event that, had it occurred in a more severe form, might have caused death.
- Requires hospitalization or prolongation of existing hospitalization;
 - Note: Any hospital admission with at least 1 overnight stay will be considered an inpatient hospitalization. An emergency room visit without hospital admission will not be recorded as a SAE under this criterion, nor will hospitalization for a procedure scheduled or planned before signing of informed consent. However, unexpected complications and/or prolongation of hospitalization that occur during elective surgery should be recorded as adverse events and assessed for seriousness. Admission to the hospital for social or situational reasons (ie, no place to stay, live too far away to come for hospital visits) will not be considered inpatient hospitalizations.
- A persistent or significant disability/incapacity or substantial disruption of the ability to conduct normal life functions;
- A congenital anomaly/birth defect; or
- An important medical event.
 - NOTE: Important medical events that may not result in death, be life-threatening, or require hospitalization may be considered an SAE when, based upon appropriate medical judgment, they may jeopardize the patient and may require medical or surgical intervention to prevent one of the outcomes listed above. Examples of such medical events include allergic bronchospasm requiring intensive treatment in an emergency room or at home, blood dyscrasias or convulsions that do not result in inpatient hospitalizations, or the development of drug dependency.

9.3 Serious Adverse Event Reporting – Procedures for Investigators

Initial Reports

All SAEs occurring from the time of informed consent until 30 days following the last administration of study drug must be reported to [REDACTED] within 24 hours of the knowledge of the occurrence (this refers to any adverse event that meets any of the aforementioned serious criteria). All SAEs that the Investigator considers related to study drug occurring after the 30-day follow-up period must be reported to the Sponsor.

To report the SAE, complete the SAE form electronically in the electronic data capture (EDC) system for the study. When the form is completed, [REDACTED] personnel will be notified electronically and will retrieve the form. If the event meets serious criteria and it is not possible to access the EDC system, send an email to [REDACTED] [REDACTED] [REDACTED] or call the [REDACTED] and fax the completed paper SAE form to [REDACTED] within 24 hours of awareness. When the EDC system becomes available, the SAE information must be entered within 24 hours of the system becoming available.

Follow-Up Reports

The Investigator must continue to follow the patient until the SAE has subsided or until the condition becomes chronic in nature, stabilizes (in the case of persistent impairment), or the patient dies.

Within 24 hours of receipt of follow-up information, the Investigator must update the SAE form electronically in the EDC system for the study and submit any supporting documentation (eg, patient discharge summary or autopsy reports) to [REDACTED] via fax or e-mail. If it is not possible to access the EDC system, refer to the procedures outlined above for initial reporting of SAEs.

9.4 Pregnancy Reporting

If a patient or female partner of a male patient becomes pregnant during the study or within 30 days of discontinuing study drug, the Investigator should report the pregnancy to [REDACTED] within 24 hours of being notified. [REDACTED] will then forward the Exposure In Utero form to the Investigator for completion.

A patient becoming pregnant while on study drug will immediately be withdrawn from the study and Early Termination study procedures will be performed.

The patient or female partner of a male patient should be followed by the Investigator until completion of the pregnancy. If the pregnancy ends for any reason before the anticipated date, the Investigator should notify [REDACTED]. At the completion of the pregnancy, the Investigator will document the outcome of the pregnancy. If the outcome of the pregnancy meets the criteria for immediate classification as an SAE (ie, postpartum complication, spontaneous abortion, stillbirth, neonatal death, or congenital anomaly), the Investigator should follow the procedures for reporting an SAE.

9.5 Expedited Reporting

The Sponsor will report all relevant information about suspected unexpected serious adverse reactions that are fatal or life-threatening as soon as possible to the FDA, applicable competent authorities in all the Member States concerned, and to the Central Ethics Committee, and in any case no later than 7 days after knowledge by the Sponsor of such a case, and that relevant follow-up information will subsequently be communicated within an additional 8 days.

All other suspected unexpected serious adverse reactions will be reported to the FDA, applicable competent authorities concerned, and to the Central Ethics Committee concerned as soon as possible but within a maximum of 15 days of first knowledge by the Sponsor.

The Sponsor will also inform all Investigators as required.

9.6 Informed Consent

All patients will be informed of the nature and purpose of the study. Patients will sign informed consent at the Screening Visit (Day -14 to Day -1), prior to any study procedures being performed.

9.7 Demographic Information

Demographic information including day, month, and year of birth; race; ethnicity; and gender will be collected at the Screening Visit (Day -14 to Day -1).

9.8 Clinical Laboratory Evaluations

All standard blood and urine tests will be performed by a central laboratory. For the purposes of this study, fasting will be defined as nothing by mouth except water for 10 hours. If the patient is not fasting, the Investigator will reschedule the visit as soon as possible but no later than 3 days. Laboratory certification (including expiration date) and normal reference ranges for all laboratories used during the study will be on file with [REDACTED] prior to study initiation. For a complete list of laboratory assessments that will be performed, see Appendix B. For blood sampling procedures, including information on blood volume, collection tubes, sample processing, storage, and shipping, see the Laboratory Manual for this study.

The Investigator must review and sign all laboratory test reports. The Investigator will be notified if laboratory values are outside of normal range and for alert values. In this case, the Investigator will be required to conduct clinically appropriate follow-up procedures.

The following analytes will be measured at the Screening Visit (Day -14 to Day -1), Baseline Visit (Day 1), and Weeks 2, 4, 8, 12, and 16:

- Standard Chemistry Panel – ALT, albumin, ALP, amylase, AST, bicarbonate, blood urea nitrogen, calcium, chloride, creatine kinase, creatinine, direct bilirubin, estimated glomerular filtration rate, gamma-glutamyl transpeptidase (GGT), glucose, inorganic phosphorus, lactate dehydrogenase, lipase, magnesium, potassium, sodium, total bilirubin, total protein, and uric acid; and
- Standard Hematology Panel – hematocrit, hemoglobin, platelets, red blood cell count, and white blood cell count and differential.

The following urinalysis analytes will be measured at the Screening Visit (Day -14 to Day -1), Baseline Visit (Day 1), and Week 12: bilirubin, blood, glucose, ketones, leukocyte esterase, microscopy, nitrate, pH, protein, specific gravity, and urobilinogen.

Hepatitis B, HBsAg, HCV, HCVAb, and HIV will be measured at the Screening Visit (Day -14 to Day -1).

A coagulation panel (aPTT, PT, and international normalized ratio [INR]) will be performed at the Screening Visit (Day -14 to Day -1) and Week 12. At the Baseline Visit (Day 1), only aPTT and PT will be performed.

A thyroid function test (TT3, TT4, FT3, FT4, TSH) will be performed at the Screening Visit (Day -14 to Day -1); Baseline Visit (Day 1), and Weeks 2, 4, 8, 12, and 16, TT3, TT4, FT3, FT4, TSH and TBG will be assessed.

A lipid panel, apolipoproteins, and lipoprotein(a) will be measured at the Screening Visit (Day -14 to Day -1). These lipids plus ApoCIII will be measured at Baseline Visit (Day 1), and Weeks 2, 4, 8, 12, and 16. A lipoprotein particle analysis will be performed at the Baseline Visit (Day 1), Week 12, and Week 16, and LDL-C will be determined by ultracentrifugation at the Baseline Visit (Day 1) and Week 12.

Sex hormone binding globulin and [REDACTED] will be measured at the Screening Visit (Day -14 to Day -1), Baseline Visit (Day 1), and Weeks 2, 4, 8, 12, and 16.

Follicle stimulating hormone, total and free testosterone, LH, CKMB, troponin I, reverse T3, ALP isoenzymes, P1NP, CTX, and fibrinogen will be measured at the Baseline Visit (Day 1), Week 12, and Week 16. Free testosterone will be calculated from total testosterone, [REDACTED], and serum albumin.

Hemoglobin A1c will be measured at the Screening Visit (Day -14 to Day -1), Baseline Visit (Day 1), and Weeks 8 and 12.

Genomic samples will be collected at the Baseline Visit (Day 1).

Backup blood samples will be collected at Baseline Visit (Day 1) and Week 12 for use if a laboratory evaluation needs to be repeated.

A urine drug screen will be performed at the Screening Visit (Day -14 to Day -1).

Proprotein convertase subtilisin/kexin type 9 and [REDACTED] will be measured at the Baseline Visit (Day 1) and at Week 12.

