5.3 Randomization and Blinding

Patients will be randomized 2:1 to study drug or placebo using a computer-generated randomization schedule prepared by [REDACTED], prior to the start of the study. The number received during randomization will identify the patient throughout the study and will be used in the eCRF.

Patients, the Sponsor, Investigators, and all site personnel involved with dispensing study medication, carrying out study procedures, evaluating patients, entering study data, and/or evaluating study data will be blinded to treatment assignment until database lock. Blinding will be accomplished by providing visually indistinguishable MGL-3196 and placebo capsules. Packaging for MGL-3196 and placebo product will be identical with the exception of a unique bottle identification number on the label.

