3.7.3 Subgroup Analysis of LDL-C

The subgroup analysis of LDL-C will be based on the mITT population. Since the analyses are for descriptive purposes only, no adjustments will be made for multiplicity.

The analysis of LDL-C will be performed based on MGL-3196 exposure group. In the analysis of LDL-C based on MGL-3196 exposure group, the patients who are taking MGL-3196 will be categorized into higher and lower exposure groups. The same ANOVA and ANCOVA models will be used, with pairwise comparisons between each exposure group versus placebo will be provided.

The analysis of LDL-C will also be performed based on SHBG group. In the analysis of LDL-C based on SHBG group, the patients who are taking MGL-3196 will be categorized into groups with higher increase or lower increase of SHBG from baseline to Week 12. Patients who are taking MGL-3196 but do not have Week 12 SHBG values will not be included. The same ANOVA and ANCOVA models will be used, with pairwise comparisons between each exposure group versus placebo to be provided.

The final dose of MGL-3196 (100 mg or 60 mg) will also be used to repeat the primary efficacy analysis. Similar to the exposure group, an analysis will be performed, but with the final dose of MGL-3196 to categorize patients who are taking MGL-3196.

The primary efficacy analysis of LDL-C will be repeated based on the following subgroups:

- Statin subgroup (80 mg Atorvastatin, 20/40 mg Rosuvastatin, or No/Low Dose Statin);
- Exposure group, SHBG group, in combination with statin subgroup;
- Gender subgroup (male, or female);
- Exposure group, SHBG group, in combination with gender subgroup;
- Baseline LDL-C value (<100 mg/dL, or \geq 100 mg/dL);
- Statin and baseline LDL-C subgroup;

- Exposure group, SHBG group, Final MGL-3196 dose group, in combination with baseline LDL-C subgroup;
- Baseline BMI value (<25 kg/m², or ≥25 kg/m²; and <30 kg/m², or ≥30 kg/m²);
- Exposure group, SHBG group, Final MGL-3196 dose group, in combination with baseline BMI subgroup;
- Average TSH between baseline and screening subgroup (<2 mIU/L, or ≥2 mIU/L);
- Exposure group, SHBG group, Final MGL-3196 dose group, in combination with average TSH between baseline and screening subgroup;

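### Investigators must sign off all laboratory reports, so on-treatment lipid and SHBG results give sites a probabilistic clue to allocation that the blinding section does not address

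*Protocol*

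**What the plan says.** - **Who sees results.** Protocol 9.8: "All standard blood and urine tests will be performed by a central laboratory", and "The Investigator must review and sign all laboratory test reports". The same section has the investigator notified of out-of-range and alert values and expects follow-up. It makes no exception for efficacy analytes.
- **What is measured on treatment.** For the lipid panel, apolipoproteins and Lp(a), Protocol 9.8 says "These lipids plus ApoCIII will be measured at Baseline Visit (Day 1), and Weeks 2, 4, 8, 12, and 16". The sentence in 9.8 that opens "Sex hormone binding globulin and" sets the same post-baseline visits for SHBG. Appendix B lists these among the clinical laboratory analytes.
- **Who must stay blinded.** Protocol 5.3 covers patients, sponsor, investigators and site staff, including those "evaluating patients, entering study data, and/or evaluating study data will be blinded to treatment assignment until database lock". The means given are indistinguishable capsules and identical packaging.
- **What is already protected.** Protocol 1.2.2 gives drug levels, and the Week 4 dose assignment that depends on them, to an unblinded clinical pharmacologist. Neither document has an equivalent for lipids or SHBG.
- **What the investigator decides.** Under Protocol 9.1.3 the investigator rates severity and "will also categorize each adverse event as to its potential relationship to study drug", as yes or no. Protocol 4.3 leaves part of withdrawal to the investigator's judgement.
- **How SHBG is used.** In SAP 3.7.3, patients on MGL-3196 "will be categorized into groups with higher increase or lower increase of SHBG from baseline to Week 12".

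**The concern.** The drug is being tested for its effect on the very results that the site is told to read. A patient whose LDL-C falls sharply by Week 2 or 4 is more likely to be on active drug, and identical capsules do nothing about that.

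The LDL-C measurement is safe: it is a central-laboratory value. Three other things are less safe.

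- **AE causality.** Safety is the first secondary objective. The factors listed in Protocol 9.1.3 include the response pattern known for the drug class, so a belief about allocation bears on the yes/no judgement.
- **Withdrawal.** SAP 3.1 accepts a lipid value only if taken less than 2 days after the last dose, and SAP 3.7.2 carries the last value forward. Withdrawal that differs by arm therefore enters the primary analysis.
- **Background lipid therapy.** Protocol 5.6.1 excludes fibrates, PCSK9 inhibitors and niacin. Neither document bars a change in statin or ezetimibe after randomisation; Protocol 6.4.2 only verifies the statin at Week 2. A visible LDL-C could prompt such a change. This is an inference from discretion, not something the documents describe.

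**Working it through.** **Inputs.** Difference 20 points in percent change in LDL-C, SD 20, 27 completers per group, 90% power, alpha 0.025 (Protocol 10.2.4, SAP 4). Allocation 2:1 (Protocol 5.3). Alpha is taken as two-sided, since the documents do not say.

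**Step 1: reproduce the plan's figure.** Normal approximation: n = 2 × (2.241 + 1.282)² × (20/20)² = 24.8, so 25 per group. Exact noncentral-t power is 89.8% at n = 26 and 91.0% at n = 27. So 27 is the smallest n that reaches 90%, and the inputs are confirmed.

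**Step 2: one LDL-C value as a clue.** Assume normal distributions with equal SD, and the Week 12 difference and SD at the visit concerned. The standardised separation is D = 20/20 = 1.

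- AUC = Φ(D/√2) = Φ(0.707) = 0.76.
- Cutting at the midpoint (a 10-point fall if the placebo mean is 0): sensitivity = specificity = Φ(D/2) = Φ(0.5) = 69%.
- Under 2:1 allocation, calling everyone active with no data is right in 2/3 = 66.7%. That is the benchmark, not 50%.
- The best rule under 2:1 cuts at t = D/2 − ln(2)/D = 0.5 − 0.693 = −0.193 SD. Accuracy = (2/3) × Φ(D − t) + (1/3) × Φ(t) = (2/3) × Φ(1.193) + (1/3) × Φ(−0.193) = 0.589 + 0.141 = 73.0%.
- In 105 patients: 0.730 × 105 = 76.7 correct guesses against 70, or about 7 more.

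**Step 3: individual patients.** For a fall of x SDs, with placebo mean 0, the odds of active drug are 2 × exp(Dx − D²/2).

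| LDL-C fall | Odds | Probability of active drug |
|---|---|---|
| 0% | 2 × e^(−0.5) = 1.21 | 55% |
| 20% | 2 × e^(0.5) = 3.30 | 77% |
| 40% | 2 × e^(1.5) = 8.96 | 90% |

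A fall of 40% or more is expected in (2/3) × 0.159 + (1/3) × 0.023 = 11% of patients.

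**Step 4: sensitivity.**

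- *Mean of Weeks 2, 4 and 8*, assuming a constant effect and between-visit correlation ρ: SD of the mean = 20 × √((1 + 2ρ)/3). For ρ = 0.9, AUC is 0.77 and accuracy 73.5%. For ρ = 0.3, AUC is 0.83 and accuracy 77.9%.
- *Assumed difference 15 to 30 with SD 10 to 20:* single-visit AUC 0.70 to 0.98.
- *Assumed larger SD with difference 20:* at SD 25 (D = 0.8), AUC 0.71 and accuracy 70.5%. At SD 30 (D = 0.67), AUC 0.68 and accuracy 69.0%.

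**Not computable.** No SHBG distribution is given for either arm, and the analyte attached to the 140% cut in SAP 3.1 is redacted. The joint information in triglycerides, ApoB and Lp(a) is also unknown, because their correlations with LDL-C are not stated.

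**The case against.** The case against is substantial, and most of it limits the point rather than removing it.

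- **The gain over chance is small.** One value moves the best guess by about 6 points (66.7% to 73.0%). SAP 3.7.4 notes high variation between screening and baseline LDL-C, so the true gain could be smaller. This stands. A reader might infer that the endpoint breaks the blind; the figures support only a probabilistic clue, strong in a minority of patients.
- **The primary measurement is objective, and the main AE tables in SAP 3.8.1 count all TEAEs whatever their causality.** This stands. The drug-related summaries remain exposed.
- **No result exists before Week 2, so not all of the 12 weeks is affected.** This stands.
- **No lipid-titration or rescue rule exists, and patients enter on a stable or maximally tolerated statin dose.** This stands, and is why the background-therapy route is labelled an inference.
- **Diet advice.** A reader might infer that it too is exposed. Protocol 9.12 schedules counselling only at screening, so on-treatment results cannot affect it.
- **A masking rule may sit in the Laboratory Manual, or the sign-off duty may mean only reports that reach the site.** Either is possible. However, Protocol 9.8 cites the manual for sample handling only, and a masking rule there would conflict with the word *all*. The protocol text would still need correcting.

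**Conclusion.** The point holds as a weakness in the stated blinding procedure. Following Protocol 9.8 as written shows investigators the on-treatment lipid and SHBG results, while Protocol 5.3 wants them "will be blinded to treatment assignment until database lock" and offers only matching capsules and packaging.

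The size is modest: AUC 0.76 and 73% best-guess accuracy against 66.7% for one LDL-C value. It rests on the plan's difference of 20 and SD of 20, normality, equal variances, and the Week 12 figures applying at earlier visits. The contribution of SHBG cannot be quantified, although the SAP grouping suggests that it is treated as a marker of drug effect.

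The documents do not support a claim that LDL-C measurement is biased or that allocation becomes known. They support a risk to AE causality and discretionary withdrawal and, by inference, to background lipid therapy. Whether sponsor staff see these results is not stated. This is a cheap improvement to make, not a flaw that invalidates the trial.

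**What to change.** Amend Protocol 5.3 and 9.8 together.

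- The central laboratory withholds post-randomisation lipid, apolipoprotein, Lp(a), ApoCIII, lipoprotein-particle and SHBG results from sites and sponsor until database lock.
- Investigator sign-off and out-of-range notification are limited to released safety reports: chemistry, liver, CK, hematology and thyroid.
- Lipid alert values go to the unblinded clinical pharmacologist already named in Protocol 1.2.2, or to the DSMB, which already reviews lipid parameters (Protocol 10.2.3).

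**Effect.** What the withheld results reveal falls to chance: AUC from 0.76 to 0.50, and accuracy from 73% to the 66.7% set by allocation. The sample size is unchanged.

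**Cost.** Protocol wording, a reporting setting at the central laboratory, and a short addition to the pharmacologist's or DSMB's remit; no new staff are needed. Sites lose sight of routine lipid values for the 12 weeks. A residual clue remains: FT4 must stay visible for safety, and Protocol 1.2.3 describes falls of about 20% in Phase 1. Lipoprotein particles are measured after baseline only at Weeks 12 and 16, so withholding them adds little during dosing and serves mainly to keep the rule uniform.
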